11.6 Safety Analyses

All safety analyses will be conducted using the Run-in Period Safety Analysis Set and the Post-Run-In Safety Analysis Set. Subjects will be analyzed according to the actual treatment received as defined in [Section 6.3](#).

11.6.1 Adverse Events

The Medical Dictionary for Regulatory Activities (MedDRA) version 21.0 or later will be used to code all adverse events (AE) to a system organ class and a preferred term. All adverse events occurring in the Run-In Period will be summarized for the Run-In Period Safety Analysis Set). All adverse events occurring during the double-blind treatment period and 30-day safety follow-up will be summarized for the Post-Run-In Safety Analysis Set. The subject incidence of AEs will be summarized for all treatment-emergent AEs, serious AEs, AEs leading to withdrawal of investigational product, and fatal AEs.

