### **6.2.1.1 Dosage, Administration, and Schedule**

Etanercept dosing in the study will follow the recommended label dosing for subjects with RA (subcutaneous injection, 50 mg once weekly). Etanercept will be provided as a 50-mg PFS (0.98 mL of a 50- mg/mL solution of etanercept). Each dose of investigational product will consist of the complete contents of 1 syringe. The injection site should be rotated with each dose. During the open-label run-in period subjects will receive 1 dose of etanercept per week (scheduled approximately 7 days apart) for 24 weeks. During the double-blind treatment period, subjects will receive 1 dose of etanercept or matching placebo per week (scheduled approximately 7 days apart) for 48 weeks. Throughout the entire trial, administration of etanercept should occur on the scheduled dose day; however, if unavoidable, it may be given earlier or later as long as the dose is not within 2 days of the next scheduled dose. If the dosing window is missed, that dose should be skipped and the reason for the missed dose must be reported on the case report form. Subsequent doses of investigational product should resume on the original schedule, calculated from the run-in visit 1 for the open label run-in period of the study and from Day 1 for the double-blind treatment period. If etanercept is to be taken the day of a study visit, it must be taken after the study visit has occurred (ie, at the subject's location on the scheduled dose day). Injections of etanercept will be administered by the subject or a caregiver. The individual administering the dose must demonstrate to the site staff that he or she is competent to correctly administer the subcutaneous doses. The first dose of etanercept in the open label run-in period and Day 1 in the double-blind treatment period must be administered at the study site. All subsequent doses will be administered at the subject's location on the scheduled dose day. Supplies of etanercept will be dispensed to subjects for administration at home. The site will instruct the subject in appropriate handling and storage of used and unused syringes and documentation of dosing in the subject diary. The dose date, quantity administered and box number of investigational product are to be recorded in each subject's diary/ electronic case report form (eCRF). Please refer to the Investigator's Brochure for the most recent safety information. A link to the United States Prescribing Information can be found in the Investigator's Brochure.

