### **7.2.9 Safety Follow-up/End of Study**

Approximately 30 days, within a window of + 7 days of the target visit date, after the last dose of investigational products, subjects will be contacted by phone by the site staff to collect any serious adverse events (refer to [Section 9](#)).

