## **9.2 Safety Event Reporting Procedures**

### **9.2.1 Adverse Events**

#### **9.2.1.1 Reporting Procedures for Adverse Events That do not Meet Serious Criteria**

The investigator is responsible for ensuring that all adverse events observed by the investigator or reported by the subject that occur after enrollment through the end of treatment period are reported using the Event CRF.

The investigator must assign the following adverse event attributes:

- Adverse event diagnosis or syndrome(s), if known (if not known, signs or symptoms),
- Dates of onset and resolution (if resolved),
- Severity (and/or toxicity per protocol),
- Assessment of relatedness to investigational product(s), and
- Action taken.

The adverse event grading scale used will be the Common Toxicity Criteria Version 4.0. The grading scale used in this study is described in [Appendix A](#). The investigator must assess whether the adverse event is possibly related to the investigational product(s). This relationship is indicated by a “yes” or “no” response to the question: Is there a reasonable possibility that the event may have been caused by the investigational product(s)?

The investigator is responsible for reviewing laboratory test results and determining whether an abnormal value in an individual study subject represents a clinically significant change from the subject’s baseline values. In general, abnormal laboratory findings without clinical significance (based on the investigator's judgment) are not to be recorded as adverse events. However, laboratory value changes that require treatment or adjustment in current therapy are considered adverse events. Where applicable, clinical sequelae (not the laboratory abnormality) are to be recorded as the adverse event.

The Investigator is expected to follow reported adverse events until stabilization or reversibility.

If the severity of an adverse event changes from the date of onset to the date of resolution, record as a single event with the worst severity on the Adverse Event Summary CRF.

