### **9.2.2 Reporting Procedures for Serious Adverse Events**

The investigator is responsible for ensuring that all serious adverse events observed by the investigator or reported by the subject that occur after signing of the informed consent through 30 days after the last day of the dosing interval of investigational product(s) are recorded in the subject’s medical record and are submitted to Amgen. All serious adverse events must be submitted to Amgen within 24 hours following the investigator’s knowledge of the event via the Event CRF.

After the protocol-required reporting period defined above, the investigator does not need to actively monitor subjects for serious adverse events. However, if the investigator becomes aware of a serious adverse event after this protocol-required reporting period, the investigator will report the event to Amgen within 24 hours following the investigator's knowledge of the event. Serious adverse events reported outside of the protocol-required reporting period will be captured within the safety database as clinical trial cases for the purposes of expedited reporting.

If the electronic data capture (EDC) system is unavailable to the site staff to report the serious adverse event, the information is to be reported to Amgen via an eSAE Contingency Report Form within 24 hours of the investigator's knowledge of the event. See [Appendix B](#) for a sample of the Serious Adverse Event Worksheet/eSAE Contingency Report Form. For EDC studies where the first notification of a Serious Adverse Event is reported to Amgen via the eSerious Adverse Event Contingency Report Form, the data must be entered into the EDC system when the system is again available.

The investigator must assess whether the serious adverse event is possibly related to any study-mandated activity or procedure. This relationship is indicated by a "yes" or "no" response to the question: "Is there a reasonable possibility that the event may have been caused by a study activity/procedure"?

The investigator is expected to follow reported serious adverse events until stabilization or reversibility.

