6.3 Basic Definitions

Age

Number of years at time of enrollment as recorded on the electronic case report form.

Investigational Product (IP)

Etanercept (or placebo for etanercept) and methotrexate (or placebo for methotrexate).

Adverse Event

In addition to the International Conference on Harmonisation (ICH) Guidance definition, an adverse event also includes any occurrence or worsening of a pre-existing medical condition.

Treatment-Emergent Adverse Event (TEAE)

TEAE during the run-in period is an adverse event that occurs on or after Run-In Day 1 (as determined by adverse event start date and pre-treatment flag NE 'Y' on the Events CRF) and up to Study Day 1. TEAE during the double-blind period is an adverse event that occurs on or after Study Day 1 (as determined by adverse event start date and pre-treatment flag NE 'Y' on the Events CRF) and up to 30 days after the last dose of IP.

Subject Incidence Rate

The subject incidence rate for a given event in a given time period is defined as the number of subjects with a first reported occurrence of the event divided by the number of subjects who entered the time period. For subjects with multiple occurrences of the same event, the event will only be counted once per subject.

Actual treatment received

Safety analyses will be performed on the Safety Analysis Sets, which analyzes subjects by actual treatment received. Actual treatment is defined below:

Actual Treatment In the Open-Label Run-In Period

• Actual Treatment = Etanercept + Methotrexate
Actual Treatment In the Double-Blind Treatment Period
If a subject receives 
- any active methotrexate and no active etanercept, then his/her actual treatment assignment is methotrexate- any active etanercept and no active methotrexate, then his/her actual treatment assignment is etanercept- any active etanercept and any active methotrexate, then his/her actual treatment assignment is etanercept + methotrexate- no active etanercept and no active methotrexate, then he/she received no actual treatment and will not be included in the safety analysis set
Actual Treatment In the Rescue Therapy Period

• Actual Treatment = Etanercept + Methotrexate

Run-in Failure

The subjects who participate in the run-in period but fulfill *any* of the below criteria are deemed not eligible for randomization and are considered run-in failures.

- SDAI > 3.3 at run-in visit 3

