10.3.4 Missing and Incomplete Dates

For any listings, missing or incomplete dates will be listed as is. No imputation will be done on incomplete stop date of an adverse event unless specified otherwise.

In the case where the start or stop date of an event or medication is missing or incomplete, the following rule will be applied:

	Missing	Imputation	Exception
Start date (AE, concomitant medication)	Day	01	Default to Study Day 1 if an event starts the same year and month as Study Day 1 and Stop date is after Study Day 1
	Day/Month	01JAN	Default to Study Day 1 if an event started the same year as Day1 and Stop date is after Study Day 1
	Day/Month/Year	No imputation	
Stop date (concomitant medication)	Day	Last day of the month	Default to the End of Study Date or the primary analysis cut-off date for ongoing subjects if the concomitant medication stopped the same year and month as the End of Study Date or primary analysis cut-off date
	Day/Month	31DEC	Default to the End of Study Date or the primary analysis cut-off date for ongoing subjects if the concomitant medication stopped the same year as the End of Study Date or primary analysis cut-off date
	Day/Month/Year	No imputation	

In case a subject dies during the study, impute the missing AE and CM end dates using the subject's date of death.

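### The SAP gives all adverse events one 30-day post-dose window although non-serious collection stops at end of treatment, and its partial-date rule can move ongoing events out of the double-blind period

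*SAP*

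**What the plan says.** **Reporting window (SAP).** Section 6.3 opens the window with "TEAE during the double-blind period is an adverse event that occurs on or after Study Day 1" and closes it with "and up to 30 days after the last dose of IP". It does not separate serious from non-serious events. Section 11.6.1 adds that "All adverse events occurring during the double-blind treatment period and 30-day safety follow-up will be summarized for the Post-Run-In Safety Analysis Set".

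**Collection window (protocol).** Under section 9.2.1.1, non-serious events "that occur after enrollment through the end of treatment period are reported using the Event CRF". Table 1 marks the adverse event row at every visit from the first run-in visit through Week 48/ET and at Disease Assessment visits, but not at the safety follow-up contact; the serious adverse event row is marked there. Section 7.2.9 says of that contact, made 30 to 37 days after last dose, that "subjects will be contacted by phone by the site staff to collect any serious adverse events". For serious events, section 9.2.2 counts its 30 days from the last day of the dosing interval, not from the last dose.

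**Incomplete start dates (SAP 10.3.4).** A start date lacking only the day is set to the first of the month. The exception, which moves it to Study Day 1, applies "if an event starts the same year and month as Study Day 1 and Stop date is after Study Day 1". Incomplete adverse event stop dates are generally not imputed; the stated exception is a subject who dies. There is no matching exception for Run-In Day 1.

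SAP Section 12, which lists departures from the protocol, mentions none of this.

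**The concern.** A table headed as covering 30 days after last dose will be read as 30 days of follow-up for every kind of event. For most of that stretch the trial does not ask about non-serious events, so an empty stretch reflects absence of collection, not absence of events.

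The length of collection can also differ between subjects. Protocol 8.1 lets a subject stop product and remain on study. If that subject keeps the visit schedule, non-serious events continue to be collected after the last dose, possibly for the full 30 days. If stopping patterns differ by arm, the arms would not be compared on the same post-dose follow-up.

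The date rule works in one direction. The events it displaces from the double-blind period are those still unresolved, which a safety reader would least want moved to the run-in.

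**Working it through.** The plan states no figure to reproduce; the check is date arithmetic, followed by a literal reading of the date rule.

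**Inputs**
- Protocol 6.2.1.1: "subjects will receive 1 dose of etanercept or matching placebo per week (scheduled approximately 7 days apart) for 48 weeks". Methotrexate or its placebo has the same weekly, 48-week schedule (6.2.2.1).
- End-of-treatment visit at Week 48, ±7 days (protocol 7.2.8); target Study Day 337 (SAP Appendix A).
- Safety call 30 days after last dose, +7 (protocol 7.2.9).
- Assumption: 48 doses taken on schedule, the first on Day 1.
- Assumption: the final dosing interval ends 6 or 7 days after the last weekly dose. Protocol 9.2.2 does not define this in days.

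**Windows for a completer**

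| Milestone | Calculation | Study Day |
|---|---|---|
| Last dose | 1 + 7 × 47 | 330 |
| End-of-treatment visit; non-serious collection ends | 7 × 48 + 1, ±7 | 337 (330 to 344) |
| SAP treatment-emergent window ends | 330 + 30 | 360 |
| Safety call, serious events only | 330 + 30 to 330 + 37 | 360 to 367 |
| Protocol serious-event window ends | 330 + 6 + 30 to 330 + 7 + 30 | 366 to 367 |

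Days in the SAP window without planned non-serious collection:
- Visit on target: 360 − 337 = 23 days, or 23/30 = 77% of the window.
- Visit at Day 344: 360 − 344 = 16 days.
- Visit at Day 330: 360 − 330 = 30 days.

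Serious-event window beyond the SAP cut-off: 366 − 360 = 6 days, or 367 − 360 = 7 days.

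**Early stopper who keeps the visit schedule.** With last dose on Day L and the final visit on Day 337, non-serious collection covers min(30, 337 − L) days of the window. It covers all 30 when L ≤ 307, against 7 days for a completer (337 − 330).

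**Date rule, Study Day 1.** Let Study Day 1 fall on day d of its month, d > 1, and let an event have that month and year, no start day, and be ongoing.
1. The default puts the start on the first of the month, d − 1 days before Study Day 1.
2. The exception needs a stop date after Study Day 1. An ongoing event has none and none is imputed, so read literally the exception fails.
3. SAP 6.3 assigns the period from the start date, so the event normally falls in the run-in.
4. The pre-treatment flag in SAP 6.3 does not rescue it. The flag is a further condition alongside the start date; it can remove an event from the window but not add one.

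The row for a missing day and month uses the same stop-date test, with a default of 1 January.

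**Date rule, Run-In Day 1.** An event in that month with no start day is set to the first, normally before the first run-in dose. By start date it then precedes both treatment-emergent windows.

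**The case against.** **A window wider than collection drops nothing.** This stands. Every non-serious event that is collected still falls inside the SAP window. Serious-only follow-up is a protocol choice that the SAP did not create. SAP 6.3 defines subject incidence as subjects with an event over subjects entering the period, so no follow-up-time denominator is distorted, and no between-arm tests of adverse events are planned. The defect is in what the tables claim to cover.

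**A reader might infer that early stoppers are fully counted and the arms are therefore not comparable.** The documents do not support that. Protocol 8.1 lets the subject agree a lesser level of follow-up, for example by telephone or from records. A subject who leaves the study has an early termination visit and then the serious-only call, much like a completer. Only stoppers who keep the visit schedule gain coverage, and no discontinuation or event rate is given. The 77% is a share of days, not of events.

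**A reader might infer that serious events after day 30 vanish from the report, or that the call must be moved.** Neither follows. SAP 11.6.1 lists serious and fatal events separately from treatment-emergent ones and does not restrict them to the treatment-emergent window. SAP 6.1 runs the Treatment Period to the End of Study date, normally the call itself. Protocol 9.2.2 obliges the investigator to report serious events through its whole window, whatever the date of the call. Only tables restricted to treatment-emergent events are exposed.

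**An ongoing event can sensibly be taken as stopping after Study Day 1.** A programmer may well do so, but the SAP does not say it. Nor does it say how an imputed day is reconciled with the pre-treatment flag. The literal rule gives the result above.

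**Conclusion.** The point holds as a minor one, confined to the safety tables. The primary endpoint is untouched.

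- **Non-serious events:** about 23 days (16 to 30) of the 30-day window lack planned collection in a completer, assuming 48 on-schedule weekly doses. Coverage may be longer in stoppers who keep their visits. The effect on arm comparisons is unquantified.
- **Serious events:** the protocol window extends about 6 to 7 days past the SAP cut-off, conditional on the assumed end of the dosing interval. Only treatment-emergent tables can lose these events.
- **Incomplete start dates:** read literally, the rule sends ongoing events to the run-in, and dates some run-in events before first dose. The number is unknown and probably small, because the event must lack a start day and fall in one of two particular months; year-only dates add cases under the same test.

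**What to change.** **SAP 6.3 and 11.6.1, non-serious events.** Define the window to end where protocol 9.2.1.1 ends collection, and state in the text and table footnotes that later follow-up holds serious events only. The alternative is to ask about all adverse events at the existing call and amend protocol 9.2.1.1 and Table 1. That costs one question per call, a small amendment and some extra event processing. It is worth doing only if still feasible: the SAP is dated 7 January 2020 and speaks of samples as already collected, so the wording change is the realistic route.

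**SAP 6.3, serious events.** Use the end of the protocol 9.2.2 window, with the last day of the dosing interval stated in days. The call timing needs no change.

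**SAP 10.3.4.** Extend the exception to a stop date after Study Day 1, or an event that is ongoing or has no stop date, in both the missing-day and the missing-day-and-month rows. Add the same exception for Run-In Day 1. The price is that some events with an unknown start day will be counted as treatment-emergent when they began earlier.

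Record these changes in SAP Section 12 where they depart from the protocol.

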11.6.2 Laboratory Test Results

Laboratory parameters with grade 3 toxicity or above may be descriptively summarized by study visit and actual treatment received during the study. Shift tables of the worst on-study laboratory toxicity based on the Common Toxicity Criteria (CTC) grade relative to baseline may be tabulated for analytes of interest (ie, creatinine, total bilirubin, AST (SGOT), ALT (SGPT), hemoglobin, platelets, WBC, absolute neutrophil count, lymphocytes) by treatment group. Modifications to CTC version 4.0 used for this analysis are described in [Appendix C](#). Subject listings of grades 3 and 4 laboratory values will be provided.

11.6.3 Vital Signs

Vital signs may be descriptively summarized in baseline disease summaries, if there are unexpected safety findings.

11.6.4 Exposure to Investigational Product

Descriptive statistics will be produced to describe the exposure to etanercept monotherapy, methotrexate monotherapy, and etanercept + methotrexate combination therapy, including number of doses, number of missed doses, and duration of dosing during the Run-in period. Descriptive statistics will be produced to describe the exposure to IP for each treatment group, including number of doses, number of missed doses, and duration of dosing.

11.6.5 Exposure to Concomitant Medication

A summary of all concomitant medications reported may be provided by preferred term as coded by the World Health Organization Drug (WHODRUG) dictionary. Only concomitant medications with a partial or complete end date are tabulated.

12. Changes From Protocol-specified Analyses

Protocol Section 10.5.2 states “Furthermore, the randomized subjects who did not receive any dose of any of the investigational products will also be considered non-responders in the primary analysis.”

However, although subjects may not receive any dose of IP, they may still have an observed SDAI value at week 48. Any randomized subjects with non-missing SDAI at week 48 will be assessed according to their original randomized treatment arm with their observed values.

Changes to Planned Covariates

We modify the listed continuous covariates by dichotomizing them at clinically meaningful cutoffs to demonstrate their influence on the primary endpoint. The following dichotomizations are used:

Age (years): < 65 years, ≥ 65 years

Disease duration: ≤ median, > median; ≤ mean, > mean

Baseline methotrexate dose: <15 mg, ≥15 mg

This dichotomous variable has been added to the pre-specified analysis because when a subject is taken off a biologic, we suspect that subjects on a higher dose of methotrexate at baseline would have a higher probability of SDAI remission than subjects on a lower dose of methotrexate at baseline. The threshold of <15 mg / ≥15 mg was selected based on the minimum and maximum methotrexate doses in this study, 10mg and 25mg, respectively.

Smoking: Never, former, current

This categorical variable has been added to the pre-specified analysis due to recognition of association of poorer arthritis disease activity with smoking.

Maintenance of SDAI remission is the primary endpoint of interest; subgroup analyses shall not be performed on secondary endpoints.

Changes to Analysis Sets

The protocol states that time to recapture SDAI remission and SDAI remission at week 48 will be evaluated for subjects that receive rescue treatment during the double-blind period. This led to the creation of the **Rescue Analysis Set** detailed in [Section 7.4](#).

However, due to the possibility of subjects fulfilling the definition of Disease-Worsening but not receiving rescue therapy, we also added a **Disease-Worsening Analysis Set**, as detailed in [Section 7.3](#).

A **Full Analysis Set** was also added to evaluate all subjects who enrolled.

The Safety Analysis Set defined in the protocol was re-named to **Post-Run-In Safety Analysis Set** for clarity, detailed in [Section 7.7](#). For the separate evaluation of safety events during Run-In, the **Run-In Safety Analysis Set** detailed in [Section 7.6](#) was also created.

Changes to Exploratory Endpoints

Biomarkers and Pharmacogenetic Parameters were listed in the protocol as exploratory endpoints. Samples were collected from this study for potential future analyses.

Exploratory endpoints not originally included in the protocol are detailed in [Section 4.1.4](#). Their addition to the exploratory analysis is due to our interest in seeing a) the Disease Activity at disease-worsening; b) the degree of improvement after rescue, even if a subject does not recapture SDAI remission; c) the proportion of disease-worsening subjects who achieve SDAI remission at Week 48. Further analyses on additional endpoints may be performed later on an ad-hoc basis.

13. Literature Citations / References

Mantel, N. (1963). Chi-square tests with one degree of freedom: Extensions of the Mantel-Haenszel procedure, *Journal of the American Statistical Association*, 58, 690-700.

<https://www.pharmasug.org/proceedings/2013/SP/PharmaSUG-2013-SP03.pdf>

Rubin, DB. Inference and Missing Data. *Biometrika* 1976; 63: 581-592.

Stokes M. E., Davis C. S., Koch G. G. (2000). *Categorical Data Analysis Using the SAS System*, Cary, NC: SAS Institute Inc. pp 75,128.

14. Appendices

Appendix A. Technical Detail and Supplemental Information Regarding Statistical Procedures and Programs

Visit Windows for Selected Efficacy and Safety Evaluations

Per protocol, visits are to be performed within 7 days of the protocol-specified study day. To allow for variations in scheduling, the following visit windows will be applied to selected efficacy and safety evaluations (ie, vital signs, laboratory evaluations) to assign a most appropriate nominal visit for the analysis (ie, analysis visit). If more than one visit falls within the same defined window, the closest visit to the target day (ie, scheduled visit week $\times 7 + 1$) will be considered for analysis. If two assessment dates are the same distance from the target day, then the latest visit will be considered for analysis. If more than one evaluation exists on the same date and time, the record with the lower accession number will be used.

Run-In Period Visits

Visit Week	Target Day	Window Definition	Interval (days)
Run-in 1	Run-in Day 1	Last evaluation prior to or on Run-In Study Day 1 and after Enrollment Date	43+
Run-in 2	Run-in Day 86	Run-in Day 44 to 125	82
Run-in 3	Run-in Day 162	Run-in Day ≥ 126	43

Double-Blind Treatment Period Analysis Visits

Visit Week	Target Day	Window Definition	Interval (days)
Baseline	Study Day 1	Last evaluation prior to or on Study Day 1 and after Run-in Visit 3*	N/A
Week 12	Study Day 85	Study Day 2 to 126	125
Week 24	Study Day 169	Study Day 127 to 210	84
Week 36	Study Day 253	Study Day 211 to 294	84
Week 48	Study Day 337	\geq Study Day 295	N/A

* Hematology and chemistry profiles were not assessed on Day 1; their Run-in Visit 3 values will be used when reporting baseline.

Visit window for SF-36 and HAQ-DI

Visit Week	Target Day	Window Definition	Interval (days)
Baseline (Day1)	1	Last evaluation prior to or on study day 1 in DB	N/A
Week 24	169	Study Day 2 to 253	252
Week 48	337	\geq Study Day 254	n/a

Time After Disease-Worsening

Let $Visit_0$ = the Analysis Visit at which a subject fulfills disease-worsening criteria, where Analysis Visit is for SDAI score and is defined in the Double-Blind Treatment Period Analysis Visits Table above. $Visit_0$ will be summarized in tables as “Disease-Worsening Baseline”.

Let $Visit_1$ represent the Analysis Visit on or after $Visit_0$.

Then DW_visit will be defined as follows:

- $DW_visit = 12$,
If $Visit_1 - Visit_0 = 0$ or 12
- $DW_visit = Visit_1 - Visit_0$,
Otherwise.

If a subject has multiple observations for the same DW_Visit , the latest observation will be used in the analysis.

Time After Rescue

“Rescue Baseline” is defined as the latest assessment on or before a subject’s rescue date.

Let $Visit_0$ = the Analysis Visit at which a subject initiates rescue, where Analysis Visit is for SDAI score and is defined in the Double-Blind Treatment Period Analysis Visits Table above.

Let $Visit_1$ represent the Analysis Visit on or after $Visit_0$.

Then $Rescue_visit$ will be defined as follows:

If subject has received rescue (Study Day Subject Received Rescue \leq Study Day):

- $Rescue_visit = 12$,
If $Visit_1 - Visit_0 = 0$ or 12
- $Rescue_visit = Visit_1 - Visit_0$,
Otherwise.

If a subject has not yet received rescue at a specific visit, $Rescue_visit$ missing.

If a subject has multiple observations for the same $Rescue_Visit$, the latest observation will be used in the analysis.

Efficacy Endpoint Scoring Algorithms

Abbreviations:

TEN28	28-joint Tender Joint Count
SW28	28-Joint Swollen Joint Count
PtGA	Patient Global Assessment
PhGA	Physician Global Assessment
ESR	Erythrocyte Sedimentation Rate

Simplified Disease Activity Index (SDAI)

The SDAI is a composite measure that sums the total number of tender and swollen 28-joint counts, the PtGA on a 0-10 scale, the PhGA on a 0-10 scale, and the CRP in mg/dL. PtGA and PhGA are collected in a 0-100 scale, so they will need to be divided by 10.

The SDAI is scored as follows:

$$\text{TEN28} + \text{SW28} + \text{PtGA}/10 + \text{PhGA}/10 + \text{CRP (mg/dL)}$$

Clinical Disease Activity Index (CDAI)

The CDAI is a further simplification of the SDAI that excludes the acute phase reactant. It sums the total number of tender and swollen 28-joint counts, the PtGA on a 0-10 scale and the PhGA on a 0-10 scale. PtGA and PhGA are collected in a 0-100 scale, so they will need to be divided by 10.

The CDAI is calculated using the following formula:

$$\text{TEN28} + \text{SW28} + \text{PtGA}/10 + \text{PhGA}/10$$

DAS28-CRP

A subject's DAS28-CRP score is calculated as follows:

$$\text{DAS28-CRP} = 0.56*\sqrt{\text{TEN28}} + 0.28*\sqrt{\text{SJC28}} + 0.36*\ln(\text{CRP}+1) + 0.014*\text{PtGA} + 0.96,$$

where CRP is measured in mg/L.

DAS28-ESR

A subject's DAS28-ESR score is calculated as follows:

$$\text{DAS28-ESR} = 0.56*\sqrt{\text{TEN28}} + 0.28*\sqrt{\text{SJC28}} + 0.70*\ln(\text{ESR}) + 0.014*\text{PtGA},$$

where ESR is measured in mm/hr.

Swollen Joint Count

The swollen joint count is an assessment of the swelling of joints using 0-1 point scale (0=none, 1=present). Joints that are marked as permanently inevaluable due to being replaced or fused are not counted as swollen for that specific visit. Joints that are marked with an intra-articular corticosteroid injection are considered swollen for that specific visit. The total swollen joint count is calculated by summing the number of joints with present swelling.

Swollen Joint Count (66)	
Temporomandibular joints (n=2)	Metacarpophalangeal joints (MCP) (n=10)
Sternoclavicular joints (n=2)	Fingers distal interphalangeal joints (DIP) (n=8)
Acromioclavicular joints (n=2)	Knees (n=2)
Shoulders (n=2)	Ankles (n=2)
Elbows (n=2)	Tarsi (n=2)
Wrists (n=2)	Metatarsal phalangeal joints (MTP) (n=10)
Fingers proximal interphalangeal joints (PIP) (n=10)	Toes proximal interphalangeal joints (PIP) (n=10)

Swollen Joint Count (28) Plus Feet and Ankles	
Shoulders (n=2)	Metacarpophalangeal joints (MCP) (n=10)
Elbows (n=2)	Proximal interphalangeal joints (Fingers PIP) (n=10)
Wrists (n=2)	Knees (n=2)
Ankles (n=2)	Tarsi (n=2)
Metatarsal phalangeal joints (MTP) (n=10)	Toes proximal interphalangeal joints (PIP) (n=10)

Swollen Joint Count (28)	
Shoulders (n=2)	Metacarpophalangeal joints (MCP) (n=10)
Elbows (n=2)	Proximal interphalangeal joints (Fingers PIP) (n=10)
Wrists (n=2)	Knees (n=2)

Tender Joint Count

The tender joint count is an assessment of the pain and/or tenderness of joints using 0-1 point scale (0=none, 1=present). Joints that are marked as permanently inevaluable due to being replaced or fused are not counted as tender for that specific visit. Joints that are marked with an intra-articular corticosteroid injection are considered tender for that specific visit. The total tender joint count is calculated by summing the number of joints with present tenderness.

Tender Joint Count (68)	
Temporomandibular joints (n=2)	Metacarpophalangeal joints (MCP) (n=10)
Sternoclavicular joints (n=2)	Metatarsal phalangeal joints (MTP) (n=10)
Acromioclavicular joints (n=2)	Toes proximal interphalangeal joints (PIP) (n=10)
Shoulders (n=2)	Knees (n=2)
Elbows (n=2)	Ankles (n=2)
Wrists (n=2)	Tarsi (n=2)
Fingers proximal interphalangeal joints (PIP) (n=10)	Hip (n=2)
Fingers distal interphalangeal joints (DIP) (n=8)	

Tender Joint Count (28) Plus Feet and Ankles	
Shoulders (n=2)	Metacarpophalangeal joints (MCP) (n=10)
Elbows (n=2)	Proximal interphalangeal joints (Fingers PIP) (n=10)
Wrists (n=2)	Knees (n=2)
Ankles (n=2)	Tarsi (n=2)
Metatarsal phalangeal joints (MTP) (n=10)	Toes proximal interphalangeal joints (PIP) (n=10)

Tender Joint Count (28)	
Shoulders (n=2)	Metacarpophalangeal joints (MCP) (n=10)
Elbows (n=2)	Proximal interphalangeal joints (Fingers PIP) (n=10)
Wrists (n=2)	Knees (n=2)

Boolean remission status (28-joint counts)

A remission measure defined as having 28-joint tender joint count ≤ 1 , 28-joint swollen joint count ≤ 1 , CRP (in mg/dL) ≤ 1 , and patient global assessment ≤ 1 .

Boolean remission status (28-joint count + feet and ankles)

A remission measure defined as having 28-joint + feet and ankles tender joint count ≤ 1 , 28-joint + feet and ankles swollen joint count ≤ 1 , CRP (in mg/dL) ≤ 1 , and patient global assessment ≤ 1 .

[figure not shown]
The joints used in 28-joint count + feet and ankles for both swollen and tender assessments are:

[figure not shown]
ankles (2), tarsi (2), metatarsal phalangeal joints (10), toes proximal interphalangeal joints (10) and tender: metatarsal phalangeal joints (MTP) (10), toes proximal interphalangeal joints (10), ankles (2), tarsi (2).

[figure not shown]
Boolean remission (66/68 joint counts)

[figure not shown]
A remission measure defined as having 68-joint tender joint count ≤ 1 , 66-joint swollen joint count ≤ 1 , CRP (in mg/dL) ≤ 1 , and patient global assessment ≤ 1 .

